15 ANALYSIS

The primary endpoint of incidence of all episodes of clinical malaria over the study period will be analysed using Cox regression models with a robust standard error to account for clustering of episodes within individuals (i.e. the Andersen-Gill extension of the Cox model). This will estimate the total effect of the interventions. The proportion of children in each group who experience one episode of malaria will be compared as a secondary outcome using Kaplan-Meier estimates: evidence for provision of complete protection through the combination of SMC and vaccination each year will be explored using recently published methods [19, 20]. For the comparison of RTS,S/AS01 plus SMC to the other interventions, a standard superiority comparison will be performed, calculating two-sided 95% confidence intervals for the hazard ratio. For the non-inferiority comparison of RTS,S/AS01 to SMC, the two-sided 95% confidence interval for the hazard ratio will be compared to a pre-specified non-inferiority margin. The trial is powered to have more than 80% power to exclude a difference of 15% in the incidence of clinical malaria over the study period, a difference considered to be clinically important. Demonstration of a smaller difference would require a substantially larger trial and is considered to be not clinically relevant. If the lower limit of the 95% does not overlap zero (i.e. it is clear that RTS,S is superior to SMC) then a superiority comparison will be performed as for the combined intervention.

A formal analysis plan will be prepared and approved by the Data Safety Monitoring Board (DSMB) appointed for the trial before the study code is broken. Both intention to treat and per protocol analyses will be undertaken. Children who received any dose of SMC or vaccine will be included in

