Children with a history of an adverse reaction to SP or AQ, known to have a serious underlying illness including known HIV infection not well controlled by treatment, having severe malnutrition (z scores < 3 SD) or known to have previously received a malaria vaccine were excluded from the trial.

Children known to have received SMC during the year prior to enrolment (either through the previous study in these districts (AZ-SMC, [NCT02211729](#)), or from the national programme) were not excluded from this study.

The list of eligible children in each country was sorted by location (village), age in months, gender and prior receipt of SMC, before assigning randomisation codes in permuted blocks of 9, to give an implicit stratification on these factors.

Sample size and Study Design

Based on the calculations described below, the trial aimed to recruit approximately 3,000 children in Burkina Faso and 3,000 in Mali (total 6,000) who would be followed for three years. A low dropout rate of around 5% per year (15% overall) was anticipated based on findings from the previous trial conducted in the same study areas.

In Burkina Faso and Mali, 2777 and 3143 children, respectively, received the first dose of study vaccine.

Superiority comparison: The trial was designed to compare the two interventions combined with either used alone. The study is powered to i) assess the statistical evidence against the null hypothesis of no difference between the combined group and either the SMC alone or RTS,S alone group, and ii) estimate the efficacy of the combined group relative to the single intervention groups with a relatively high degree of precision. This latter aspect is important because if the combined intervention is to be used in practice, it is necessary to show that adding RTS,S/AS01 to SMC has a clinically significant benefit.

After two years of follow-up, incidence of clinical malaria, as defined below, was approximately 200 cases per 1000 child-years at risk. With approximately 2000 individuals in each arm, if the

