incidence is at least 30% lower in the combined group, there is very high power over the three years of the study (close to 100%) to reject the null hypothesis of no difference between the combined group and the single treatment groups. If efficacy of the combined group relative to either of the other groups is at least 30%, there will be 90% power for the lower limit of the 95% confidence interval to exclude 15%, i.e. to address point ii) above, establishing that the protection from the combined group is at least 15% better than SMC or vaccination alone.

Non-inferiority comparison: SMC for four months of the year has an efficacy, assuming receipt of all four monthly cycles, of about 85% during this 4-month period. If, without intervention, the peak four months of malaria incidence would account for 60% of annual cases (with the other 40% falling during the other months) this equates to an efficacy over 12 months of at least 50%. The non-inferiority margin is the largest reduction in this efficacy that policy makers would be likely to accept if RTS,S/AS01 was to replace SMC, taking into account potential advantages of RTS,S over SMC in terms of ease of delivery and the potential to sustain high levels of coverage. A reduction in annual efficacy from 50% to 40% was considered the largest difference that would be likely to be acceptable. This translates to a 20% greater incidence in the RTS,S/AS01-alone arm compared to the SMC-alone arm. With the anticipated incidence rates, there is adequate power to reject a smaller margin, as detailed in the protocol. However, 20% was considered the largest difference that would be considered unimportant.

The study has 80% power to exclude, at the 2.5% significance level, a relative difference in the incidence of clinical malaria of 20% over the three year study period between the RTS,S/AS01 and SMC alone groups, if these two interventions were equally effective. Evidence of the effectiveness of the reference group – SMC alone - in these areas comes from clinical trials in Mali and Burkina Faso in 2009 (1, 2), and more recently in case-control studies conducted in both countries in 2016. In the previous AZ-SMC trial in these two districts (3), the prevalence of molecular markers of resistance to SP and AQ were very low, and the curative efficacy of SP+AQ over 28 days was above 95% in both areas (Cairns et al., submitted).

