Hypothesis testing will follow the closed testing procedure, whereby there is initially a test of the null hypothesis that the incidence in the three groups is the same. If this is rejected at the 5% level, pairwise comparisons will be done also using a 5% significance level. Pairwise comparisons can be considered statistically significant only if the overall null hypothesis is rejected.

For the non-inferiority comparison described above, we will calculate two-sided 95% confidence intervals, equivalent to the use of a one-sided significance level of 2.5%, as is recommended (4). To illustrate the level of confidence with which non-inferiority can be declared, we will plot the point estimate for the hazard ratio with two-sided 90, 95 and 99% confidence intervals, and the non-inferiority margin.

Database and randomisation codes

Data have been collected using electronic case record forms (eCRF) developed using Open Data Kit (ODK) software. Tablet PCs are used to document all intervention contacts and all active surveillance contacts such as the weekly and cross-sectional surveys. For passive case detection, tablet PCs loaded with eCRFs are available at all study health centres that provide treatment. Data are transferred from the eCRFs held in the research sites to a central data management

team. Automatic checks are performed on clinical and laboratory forms to ensure that they are complete and contain valid responses prior to transferring data. Further checking and cleaning of the data (including checks for duplicate entries, consistency and range checks of variables) is then carried out by the data management teams in Burkina Faso and Mali using MS Access.

The consistency of merges between different database tables will be undertaken blind to randomisation group. The analysis databases and analysis programmes (written as Stata do files) will also be prepared for the primary and key secondary analyses before the randomisation code is broken.

A final version of the database for analysis, following approval by the Data and Safety Monitoring Board (DSMB) will be burned to CD and a copy sent to the chair of the DSMB for archiving.

The randomisation codes will only be released when the final database is ready and authorisation is given by the DSMB.

All data used for analysis of the main trial report will be annotated and archived. Stata code used for the analyses will also be archived.

Primary Endpoint

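### The SAP's 80% non-inferiority power and 90% superiority power do not fit one variance model, and its assurance about a smaller margin holds at the protocol's 300 per 1000 but probably not, for 15%, at the 200 per 1000 it reports

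*Combined protocol and SAP*

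**What the plan says.** All the SAP statements are in revision 1, Sample size and Study Design.

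- Observed rate: after two years, "incidence of clinical malaria, as defined below, was approximately 200 cases per 1000 child-years at risk".
- Superiority: with about 2,000 children per arm and a true efficacy of the combined arm of at least 30%, "there will be 90% power for the lower limit of the 95% confidence interval to exclude 15" per cent.
- Margin: a fall in annual efficacy from 50% to 40% is taken as the largest acceptable. "This translates to a 20% greater incidence in the RTS,S/AS01-alone arm compared to the SMC-alone arm". The SAP adds: "With the anticipated incidence rates, there is adequate power to reject a smaller margin, as detailed in the protocol".
- Non-inferiority: "The study has 80% power to exclude, at the 2.5% significance level, a relative difference in the incidence of clinical malaria of 20" per cent over three years, "if these two interventions were equally effective". The level is one-sided: "we will calculate two-sided 95% confidence intervals, equivalent to the use of a one-sided significance level of 2.5%, as is recommended".

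The final protocol, section 6, assumes 300 cases per 1000 children per year. Over three years it gives 80% power to exclude 13.9% and 90% power to exclude 16.1%. Section 15 says: "The trial is powered to have more than 80% power to exclude a difference of 15% in the incidence of clinical malaria".

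Neither document states a design effect or between-child dispersion for any of these powers.

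**The concern.** Power falls as a non-inferiority margin shrinks. At one incidence rate and one variance, 80% power at 20% therefore cannot stand beside 80% or more at any smaller margin, yet the SAP gives its assurance about a smaller margin just before it prints the 80%. The observed rate is also a third below the rate behind the protocol's figures.

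Separately, the non-inferiority and superiority powers come from the same trial, and the superiority contrast has fewer events in one arm. Its standard error should be no smaller than that of the non-inferiority contrast, but the printed powers require it to be smaller.

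What is at stake is how a reader judges the trial's resolution. Non-inferiority is one of two objectives that the SAP ranks equally. The protocol describes 15% as clinically important, the SAP tests against 20%, and the assurance tells readers that a tighter margin was within reach.

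**Working it through.** **Inputs.** From the SAP: 200 per 1000 child-years; about 2,000 per arm; three years; margin HR 1.20 with true HR 1; one-sided 2.5%; superiority with true HR 0.70, to exclude HR 0.85. From the protocol: 300 per 1000; 80% at 13.9%; 90% at 16.1%. Normal quantiles: 1.960 + 0.842 = 2.802 for 80% power, and 1.960 + 1.282 = 3.242 for 90%. Throughout, power = Φ(distance on the log scale / SE − 1.960).

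**1. Try to reproduce the SAP's powers with no overdispersion.** Events per arm = 2,000 × 3 × 0.2 = 1,200.
- Non-inferiority: SE = √(2/1,200) = 0.0408. Power at 20% = Φ(0.1823/0.0408 − 1.960) = 99.4%; at 15% = Φ(0.1398/0.0408 − 1.960) = 92.8%.
- Superiority: SE = √(1/1,200 + 1/840) = 0.0450. Power = Φ(0.1942/0.0450 − 1.960) = 99.1%.

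With 5,920/3 ≈ 1,973 per arm and a flat 15% loss (about 1,006 events), these become 98.3%, 88.0% and 97.7%. Neither printed power is reproduced, so each must contain an unstated variance inflation.

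**2. Standard errors that the printed powers imply.**
- 80% at 20%: SE = ln(1.20)/2.802 = 0.0651. Inflation at 1,200 events: 0.0651² / (2/1,200) = 2.54.
- 90% to exclude 15%: SE = ln(0.85/0.70)/3.242 = 0.0599. Inflation: 0.0599² / (1/1,200 + 1/840) = 1.77.

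**3. Can both be exact?** With common sample size, rate and dispersion, the ratio of superiority to non-inferiority variance lies between 1 (between-child variation dominates) and (1 + 1/0.7)/2 = 1.214 (event counts dominate).
- From 80% non-inferiority: superiority power is Φ(0.1942/(0.0651 × √1.214) − 1.960) = 77% up to Φ(0.1942/0.0651 − 1.960) = 85%. The SAP prints 90%.
- From 90% superiority: non-inferiority power at 20% is Φ(0.1823/0.0599 − 1.960) = 86% up to Φ(0.1823/(0.0599/√1.214) − 1.960) = 92%. The SAP prints 80%.

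**4. The protocol at its own rate.** SE = ln(1.139)/2.802 = 0.0465; the 16.1% figure gives ln(1.161)/3.242 = 0.0461, in good agreement. Power at 15% = Φ(0.1398/0.0465 − 1.960) = 85%. Section 15 is right on its planning inputs.

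**5. Power at 15% at the SAP's 200 per 1000.**

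| Source of variance | SE | Power at 15% | Power at 20% |
|---|---|---|---|
| Protocol, constant inflation: 0.0465 × √1.5 | 0.0569 | 69% | 89% |
| Protocol, constant between-child part: √(2/1,200 + 0.0465² − 2/1,800) | 0.0521 | 77% | 94% |
| SAP superiority figure, upper SE | 0.0599 | 65% | 86% |
| SAP superiority figure, lower SE: 0.0599/√1.214 | 0.0544 | 73% | 92% |
| SAP 80% at 20%, taken as exact | 0.0651 | 57% | 80% |
| No overdispersion | 0.0408 | 93% | 99% |

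**6. When would 15% have 80% power?** The SE must be at most ln(1.15)/2.802 = 0.0499, an inflation of at most 0.0499² / (2/1,200) = 1.49. Power at 20% is then at least Φ(0.1823/0.0499 − 1.960) = 95%, and superiority power at least Φ(0.1942/(0.0499 × √1.214) − 1.960) = 94%. Both printed SAP powers would then be too low.

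**The case against.** The strongest reply is that the sentence about a smaller margin is conditional. It refers to anticipated rates and points to the protocol, which anticipated 300 per 1000. Read that way it is accurate (step 4). This stands. A reader might infer that protocol section 15 is wrong; the documents do not support that, because a lower rate observed later does not falsify a planning statement.

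A reader might also take 57% as the trial's power at 15%. It is only what the printed 80% implies if exact, and it is the least favourable of several values. The protocol's variance carried to 200 per 1000 gives 89–94% at 20%, which suggests that the printed 80% is understated. That variance would still support some margin below 20%: exp(2.802 × 0.0569) − 1 = 17% or exp(2.802 × 0.0521) − 1 = 16% at 80% power. The SAP names no figure for its smaller margin.

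Nor can one say that a printed power must be wrong on every reading. If 80% is a floor, it can sit beside 90% for superiority. The non-inferiority paragraph restates no rate, so common inputs are an assumption. Against this, the SAP gives the 80% as a plain figure, whereas the protocol says when it means more than 80%.

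Finally, a reader might suspect that 20% was chosen because power was short. The SAP justifies it by retained efficacy, and nothing in the documents shows otherwise. The decision rests on the confidence interval, so no test or estimate is affected.

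**Conclusion.** The point holds as a matter of consistency and currency. As point figures with a common sample size, rate and dispersion, the SAP's 80% and 90% cannot both be exact: the first implies 77–85% where 90% is printed, the second 86–92% where 80% is printed. The stated inputs alone give about 99% for both, so the variance behind each figure is undisclosed and differs between them (inflation 2.54 against 1.77 at 1,200 events per arm).

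The assurance about a smaller margin is sound at 300 per 1000 and out of date at 200 per 1000. For the protocol's 15%, power is then about 69–77% with the protocol's variance and 65–73% from the superiority figure. It reaches 80% only if overdispersion is low, and in that case both printed SAP powers are too low. The true dispersion is not in the documents, so no single value can be called the trial's power at 15%.

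**What to change.** In the SAP, recompute both powers from one variance model: about 1,973 children per arm, actual person-years, 200 per 1000, and one between-child dispersion estimated from the pooled blinded data. Print the dispersion, the superiority power, and the non-inferiority power at 15% and at 20%. Restate the sentence on a smaller margin as applying to the protocol's 300 per 1000, with the updated power at 15% beside it. Protocol section 15 needs only a note that its figure rests on that planning rate.

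The cost is one calculation and a few sentences. Margin, sample size, tests and estimates are unchanged. The statement about 15% will probably read less favourably; the printed 80% at 20% may well rise.

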2.1 Morbidity events detected passively at study health centres and hospitals

As for the primary outcome, episodes of the outcomes listed below which occur within 7 days of a previous event of the same type will be discounted. No adjustment is necessary to the person-time at risk (11).

2.1.1 **Clinical malaria with *P. falciparum* parasitaemia of any density.** Defined as an episode of fever (either measured temperature $\geq 37.5^{\circ}\text{C}$, or a history of fever within the past 48 hours), and a positive blood film for *P. falciparum* parasites. This includes hospitalisations for malaria meeting the above criteria (i.e. fever or history of fever, plus slide confirmed *P. falciparum* malaria of any density).

2.1.2 **Clinical malaria confirmed by rapid diagnostic test.** Defined as an episode of fever (either measured temperature $\geq 37.5^{\circ}\text{C}$, or a history of fever within the past 48 hours), and a positive rapid diagnostic test (RDT).

2.1.3 **Clinical malaria with non-falciparum parasitaemia of any density.** Defined as an episode of fever (either measured temperature $\geq 37.5^{\circ}\text{C}$, or a history of fever within the past 48 hours), and a positive blood film for non-falciparum *Plasmodium* parasites.

2.1.4 **Clinical malaria with *Plasmodium spp.* infection of any density.** Defined as an episode of fever (either measured temperature $\geq 37.5^{\circ}\text{C}$, or a history of fever within the past 48 hours), and a positive blood film for any *Plasmodium spp.* parasites (i.e. including *P. falciparum*).

2.2 Severe outcomes detected passively at study health centres and hospitals, and through verbal autopsies

For all hospital admissions and deaths, the primary diagnosis by a study physician was reviewed by a second independent clinician. A third clinician reviewed cases of disagreement to reach a consensus primary diagnosis. All verbal autopsies were also reviewed by the same process to obtain a consensus cause of death.

2.2.1 Hospital admissions due to any cause

2.2.2 Hospital admissions excluding those due to external causes or surgery

2.2.3 **Hospital admissions due to malaria.** Defined as hospital admissions where malaria was the primary diagnosis, supported by a positive blood smear, or positive RDT if no blood smear result was available. Additional analyses of children who meet the WHO criteria for a diagnosis of severe malaria including those with a) cerebral malaria, b) severe anaemia and c) other forms of severe malaria will be undertaken.

2.2.4 The incidence of blood transfusions in study hospitals

2.2.5 Deaths due to any cause

2.2.6 Deaths due to any cause excluding external causes and surgery

2.2.7 **Deaths due to malaria.** Defined as hospital admissions resulting in death, where malaria was recorded as the primary cause of death, and where parasitology results did not

exclude malaria (i.e. a positive blood smear, if a slide result was available, or a positive RDT if no slide was done). Deaths in the community will also be included when malaria is assigned as the primary cause of death by verbal autopsy.

2.3 Outcomes measured at weekly surveys

A subset of children were selected to be sampled for parasitaemia during weekly surveys. Systematic random sampling, from lists sorted on age, was used to allocate children to be sampled in not more than one week per year, such that the sample of 24 children in each week, in each country was balanced with respect to age and treatment group. Results from the weekly surveys will be analysed and presented separately for each malaria transmission season (2017, 2018 and 2019).

2.3.1 The prevalence of asexual stage *P. falciparum* infection of any density detected during the weekly home visits.

2.3.2 The prevalence of asexual stage *P. falciparum* infection with a density ≥ 5000 per ul detected during the weekly home visits.

2.3.3 The arithmetic mean *P. falciparum* parasite density, including samples which are parasite negatives as having a density of zero.

2.4 Outcomes measured at cross-sectional surveys at the end of the malaria transmission season

For each of the outcomes below, results will be analysed and presented separately for each malaria transmission season (2017, 2018 and 2019).

2.4.1 The prevalence of asexual stage *P. falciparum* infection of any density

2.4.2 The prevalence of asexual stage *P. falciparum* infection with density ≥ 5000 per ul

2.4.3 The prevalence of sexual stage *P. falciparum* infection (i.e. gametocytes)

2.4.4 The arithmetic mean *P. falciparum* parasite density, including samples which are parasite negatives as having a density of zero.

2.4.5 The prevalence of asexual stage infection of non-falciparum *Plasmodium* species.

2.4.6 The prevalence of sexual stage infection (i.e. gametocytes) of non-falciparum *Plasmodium* species.

2.4.7 The mean haemoglobin concentration in g/dL.

2.4.8 The prevalence of anaemia, defined as measured Hb < 10 g/dL.

2.4.9 The prevalence of moderate anaemia, defined as measured Hb < 7 g/dL.

2.4.10 The prevalence of severe anaemia, defined as measured Hb < 5 g/dL.

2.5 Other secondary outcomes

2.5.1 The prevalence of molecular markers of resistance to SP and AQ in children with *P. falciparum* infection, among samples collected at the final cross-sectional survey in December 2019. These include the dhfr 51-59-108 triple mutation, dhps-A437G, and dhps-K540E mutations for resistance to SP, and the pfcr1 K76T and pfmdr1 N86Y mutations for resistance to AQ.

2.5.2 The percentage of children with asymptomatic *P. falciparum* parasitaemia at the cross-sectional survey in December 2019, who, when treated with SP+AQ, have an adequate clinical and parasitological response (ACPR) after 28 days.

Serious Adverse Events

In addition to the comparison of incidence rates described above (section 2.2), serious adverse events (SAEs) defined as hospitalisations or death, occurring at any time during the study will be tabulated by study group according to their cause.

Safety signals from the RTS,S/AS01 phase 3 studies

The incidence of meningitis has been very low in the study cohort, with no events up to the 30th November 2019. A 95% confidence interval for the incidence rate of meningitis among children vaccinated with RTS,S/AS01 will be calculated.

The incidence of cerebral malaria among children vaccinated with RTS,S/AS01 will be investigated by comparing the RTS,S/AS01 groups with the SMC alone group, controlling for SMC status using an indicator variable. Cox regression will be used to obtain the hazard ratio and its 95% confidence interval.

The incidence of febrile convulsions not related to malaria or another obvious cause among children vaccinated with RTS,S/AS01 will be investigated as for cerebral malaria, i.e. by comparing the RTS,S groups with the SMC alone group, controlling for SMC status using an indicator variable. Cox regression will be used to obtain the hazard ratio and its 95% confidence interval. The subset of febrile convulsions that occurred within 7 days of vaccination will also be analysed.

An exploratory analysis will investigate if there is any evidence that RTS,S/AS01 increases mortality in girls. This will compare the incidence of deaths using Cox regression, with an interaction between a dummy variable indicating receipt of RTS,S/AS01 and gender. The Wald test p-value for the interaction term will be used to assess evidence for effect modification. This model will also include a dummy variable for SMC to adjust for SMC receipt. This will enable the female: male mortality ratio and its 95% confidence interval to be calculated separately for RTS,S/AS01 recipients, and non-recipients. We will use indicator variables to obtain the ratio of these ratios, with the 95% confidence interval. We will also present the mortality ratio for RTS,S recipients versus non-recipients separately for males and females. Since it is hypothesised that this effect may be age-dependent, we will also carry out these analyses restricted to the period after the first booster dose.

Outcomes measured among school-age children

To help interpret results obtained in study children, end of season surveys have also been conducted among school-age children in the study areas. The following outcomes will be calculated for school-age children.

- 3.1. The prevalence of asexual stage *P. falciparum* infection of any density
- 3.2. The prevalence of asexual stage *P. falciparum* infection with a density ≥ 5000 per ul
- 3.3. The arithmetic mean *P. falciparum* parasite density, including samples which are parasite negatives as having a density of zero.

Analysis populations and person-years at risk

The primary analysis will be by modified intention to treat (mITT). The mITT population will include all children who were screened and who received the first dose of RTS,S/AS01 or control

vaccine, irrespective of the number of doses of subsequent vaccines or SMC/SMC placebo received.

Children will contribute time at risk from the date of the first vaccination contact in 2017, until 1) the date observation formally ended (31st March, 2020), 2) the date last seen if lost-to-follow-up (LTFU), 3) the date of permanent exit from the study area, or 4) the date of death.

Children who temporarily left the study area with known exit and re-entry dates will have the corresponding person-time excluded from the analysis by intention to treat (and per protocol, if leaving the study area does not result in missed treatments).

As a secondary analysis, the primary outcome will also be analysed per protocol (PP). The PP population will be defined separately for each year of the study. Children who were vaccinated at all scheduled vaccination contacts in a particular year (3 in 2017, 1 in 2018, 1 in 2019) and who, in the same year, were also seen at the first SMC/SMC placebo contact each month (4 per year) will be considered as 'per protocol' for that year. Children who attended for SMC administration but who did not receive SMC because they had malaria and were referred for treatment will be included in the per protocol analysis.

'Per protocol' is defined differently for the two interventions (vaccination and SMC). For vaccination, a child must have *received* all vaccination doses that year; for SMC a child must only have *attended* all SMC contacts that year. This difference is necessary because the primary outcome of the trial (clinical malaria) can result in a specific SMC dose being missed permanently, whereas if a child had malaria at the time of vaccination, catch-up was attempted later in the season. The per protocol conditions will be applied equally to all three groups, i.e. to be considered as per protocol, a child must have received all doses of vaccine AND attended all SMC contacts, irrespective of which of these were active and placebo.

All secondary outcomes will be analysed by modified intention to treat as described above.

Trial profile

The trial profile will show the number of individual children enumerated at the initial census, the number of children eligible, and the number of children for whom consent was obtained. Reasons that children seen at the census were not eligible to join the study will be tabulated.

The profile will also show, for all the eligible children seen at the census who were randomised, the number of children seen at the first study contact who received the first dose of vaccine and who joined the study. Reasons that children did not attend the first study contact for vaccination will be tabulated.

The number of children who exited the study population by the end of the first, second and third year of the study will be shown, with reasons (where known) tabulated.

Uptake of the study interventions will be summarised, including:

- the number that received different combinations of vaccine doses;
- the distribution of the interval between doses;
- the number that received 0,1,2,3,4 SMC treatments each year;

- the actual timing of SMC cycle 1 in relation to the malaria transmission season;
- the mean and range of the intervals between the monthly SMC courses;
- the adherence to daily doses of SMC each month

Separate profiles will be produced for each of the two trial centres.

Statistical methods

Reference group

As SMC is the current standard of care, the SMC alone group will be considered as the reference group for comparisons with RTS,S/AS01 alone, and the combined group. Comparisons will also be made between RTS,S/AS01 alone and the combined group.

Primary endpoint

The hazard ratio for the primary outcome will be estimated using Cox regression models, with a robust standard error (i.e. the Andersen-Gill extension of the Cox model) to account for potential clustering of episodes within children. The Efron method will be used for tied event times.

The timescale will be calendar time, starting from 1st April 2017, i.e. allowing delayed entry according to the precise timing of the first vaccination contact. This ensures that risk sets in the Cox models are comparable with respect to the timing of onset of transmission each year, and the timing of SMC. Due to variable timing in vaccine dose 1 in 2017, this would not be the case if the data were analysed on the time in study timescale.

Nelson-Aalen Cumulative hazards will be plotted for each group to show the mean number of events per child during the study and the timing of events, and Kaplan Meier failure estimates will be plotted to show the risks during the study.

As recommended in the updated CONSORT guidelines (8), the incidence rate differences (IRD) will also be calculated, as this gives an indication of the reduction in incidence attributable to the interventions, i.e. the absolute public health impact in similar contexts. The IRD will be calculated using ordinary least squares regression of transformed variables, as described by Xu et al. (9). This method uses a robust standard error and controls for unequal follow-up time, as well as quantitative or multiple covariates. To aid interpretation, the risk of the primary outcome will also be estimated from the Kaplan-Meier estimate of the risk.

Secondary endpoints

Secondary outcomes which are passively detected events, will be analysed in a similar way as for the primary outcome, i.e. estimating the hazard ratio using Cox regression with a robust standard error.

The prevalence ratio of secondary endpoints measured at the weekly survey (aggregated into three-month periods), and at end of season surveys (including *P. falciparum* parasitaemia, anaemia, etc) will be estimated using Poisson regression, with a robust standard error for the individual, as described in Zou, 2004 (10).

Linear regression models will be used to compare mean haemoglobin concentration between the groups.

Arithmetic mean parasite densities (including in the calculation samples which are parasite negatives, as having density of zero), will be compared between arms using Poisson regression with a robust standard error.

Covariates

All analyses (primary outcomes and secondary outcomes) will adjust for study country only (Burkina Faso or Mali).

For the primary outcome, we will also build a model adjusting for the following potential confounders:

- Age at enrolment
- Child's Sex
- Bednet use at baseline

Pre-specified subgroup analyses, interactions and exploratory analyses

As described above, the primary analysis will be pooled across the two study centres, stratified by (i.e. adjusted for) country. Efficacy (ratio and difference) measures will be presented for both sites combined. Investigation of any differences in intervention effects between the centres (formally, evidence for an interaction between intervention group and study centre) is pre-specified due to possible differences in performance of these interventions under different malaria transmission intensity. All outcomes will, therefore, also be tabulated by centre, and site specific efficacy estimates will be presented.

Investigation of differences between study groups in successive years of the study is also pre-specified, because it is possible that the efficacy of RTS,S/AS01 booster doses is different to the primary series. This will be assessed by exploring evidence for an interaction between intervention group and study year (2017-18, 2018-19, 2019-20).

Finally, evidence for effect modification by age at enrolment will be explored. It is possible that vaccination will perform differently according to the extent of prior exposure to malaria. Of particular interest are participants who were young infants at the time of the first vaccination in 2017, as they may have had no exposure to malaria prior to enrolment in the trial.

Pre-specified Secondary analyses

As this is the first trial of seasonal vaccination, a number of secondary analyses are planned to investigate the effect of malaria event history, completeness of protection and protection over time. Lexis expansion will be used to stratify person-time since vaccination. This will enable regression splines to be fitted to obtain smooth estimates of protection over time from RTS,S/AS01.

Further analyses will explore the changing relative benefits of SMC and RTS,S/AS01 with age and transmission intensity (by comparing efficacy profiles with age between Burkina Faso, which has higher incidence rates, with Mali).

Ancillary studies to be reported separately

1. Evaluation of anti-CSP antibody concentrations obtained before and after priming and after each booster dose, determined in a sub-sample of children, and the relation of antibody concentration following vaccination to the subsequent risk of malaria.
2. The effect of the intervention on nutritional status at the end of season cross-sectional surveys.

Analysis of the preference of participants for an injection of vaccine or for multiple rounds of SMC was scheduled to take place during the last few months of this phase of the study. However, this has had to be postponed because of travel restrictions imposed by the COVID-19 crisis.

On the advice of the steering committee and one of the trial funders (PATH) the economic analysis of the two approaches to malaria control will be undertaken in the second year of an extension study. The extension study will observe children up to the age of five years when they will no longer be eligible to receive SMC, rather than stopping follow-up after three years, as had been proposed initially.

Planned main tables for published report

Table 1: Incidence of the primary outcome: number of cases of clinical malaria; person-years at risk (PYAR); rates per 1000 person-years; and P-values from tests of homogeneity among all study children. Results will also be shown by country with results of the test of interaction by country.

	No. children	PYAR	No. events	Rate/1000 (95% CI)	Rate Ratio (95% CI)		Test of homogeneity ¹	Interaction by Country
All children								
SMC	2000	6000.0	1333	180.0 (120.0, 240.0)	(Reference)		P=0.0	
RTS,S	2000	6000.0	1333	180.0 (120.0, 240.0)	1.00 (0.90, 1.10)	Reference		
Combined	2000	6000.0	1333	180.0 (120.0, 240.0)	1.00 (0.90, 1.10)	1.00 (0.90, 1.10)		
Total	6000	18000.0	4000	180.0 (120.0, 240.0)	-	-	-	
Burkina Faso								
SMC	2000	6000.0	1333	180.0 (120.0, 240.0)	(Reference)		P=0.0	P=0.0
RTS,S	2000	6000.0	1333	180.0 (120.0, 240.0)	1.00 (0.90, 1.10)	Reference		
Combined	2000	6000.0	1333	180.0 (120.0, 240.0)	1.00 (0.90, 1.10)	1.00 (0.90, 1.10)		
Total	6000	18000.0	4000	180.0 (120.0, 240.0)	-	-	-	
Mali								
SMC	2000	6000.0	1333	180.0 (120.0, 240.0)	(Reference)		P=0.0	
RTS,S	2000	6000.0	1333	180.0 (120.0, 240.0)	1.00 (0.90, 1.10)	Reference		
Combined	2000	6000.0	1333	180.0 (120.0, 240.0)	1.00 (0.90, 1.10)	1.00 (0.90, 1.10)		
Total	6000	18000.0	4000	180.0 (120.0, 240.0)	-	-	-	

Numbers are included only to give an idea of layout / spacing.

Table 2: Incidence of the primary outcome by study year: number of cases of clinical malaria; person-years at risk (PYAR); rates per 1000 person-years; and P-values from tests of homogeneity among all study children. The results of the test of interaction by study year will also be shown.

	No. children	PYAR	No. events	Rate/1000 (95% CI)	Rate Ratio (95% CI)		Test of homogeneity ¹	Interaction by Year
Study Year 1								
SMC	2000	6000.0	1333	180.0 (120.0, 240.0)	(Reference)		P=0.0	
RTS,S	2000	6000.0	1333	180.0 (120.0, 240.0)	1.00 (0.90, 1.10)	Reference		
Combined	2000	6000.0	1333	180.0 (120.0, 240.0)	1.00 (0.90, 1.10)	1.00 (0.90, 1.10)		
Total	6000	18000.0	4000	180.0 (120.0, 240.0)	-	-	-	
Study Year 2								
SMC	2000	6000.0	1333	180.0 (120.0, 240.0)	(Reference)		P=0.0	P=0.0
RTS,S	2000	6000.0	1333	180.0 (120.0, 240.0)	1.00 (0.90, 1.10)	Reference		
Combined	2000	6000.0	1333	180.0 (120.0, 240.0)	1.00 (0.90, 1.10)	1.00 (0.90, 1.10)		
Total	6000	18000.0	4000	180.0 (120.0, 240.0)	-	-	-	
Study Year 3								
SMC	2000	6000.0	1333	180.0 (120.0, 240.0)	(Reference)		P=0.0	
RTS,S	2000	6000.0	1333	180.0 (120.0, 240.0)	1.00 (0.90, 1.10)	Reference		
Combined	2000	6000.0	1333	180.0 (120.0, 240.0)	1.00 (0.90, 1.10)	1.00 (0.90, 1.10)		
Total	6000	18000.0	4000	180.0 (120.0, 240.0)	-	-	-	

Numbers are included only to give an idea of layout / spacing.

Similar tables will be used to report the incidence of passively detected secondary outcomes.

Table 3: Prevalence of *P. falciparum* infection at the end of malaria transmission season surveys: number of children tested; number with the outcome of interest; prevalence (95% CI); prevalence ratio (95% CI) and P-values from tests of homogeneity will be shown.

	No. children with result	No. with outcome	Prevalence (95% CI)	Prevalence Ratios (95% CI)		Test of homogeneity ¹
P. falciparum infection						
